20 TREATMENT

Randomization and Blinding

This study follows an open-label randomization design. A randomization scheme will be generated by the Data Management Center prior to the initiation of the study.

Study Drugs

Every attempt will be made to pre-position the study drugs under active study at the participating sites' pharmacies in advance of enrollments. Randomization of individual patients to a given study drug will only occur when there is sufficient quantity of that drug to complete a full treatment course for those individuals.

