26.4.1 Causality

The likelihood that the SAE is related to the study agent will be assessed by the investigator considering by the following simplified categorization. Due to the severity of Ebola illness and limitations of an ETU, further detailed breakdown will not occur:

Reasonable Possibility

- reasonable temporal relationship
- little evidence for a more likely alternative etiology

No Reasonable Possibility

• does not have a reasonable temporal relationship

OR

• reasonable evidence for a more likely alternative etiology

Investigator Reporting Responsibilities to the Sponsor

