	3.9.4 LATE CLINICAL SYMPTOMS	

1 Introduction

This document describes the content proposed for the primary statistical analysis of PREVAIL II, the randomized controlled trial of ZMapp in acute Ebola virus disease (EVD). The focus is on analyses that address the major randomized comparisons for key safety, tolerability and efficacy outcome measures, including those needed to address the study's primary objective as well as the main secondary objectives. This analysis plan therefore includes the key analyses for presentation or publication of the primary conclusions of the study.

2 Study Overview

The study protocol is a master protocol for the evaluation of multiple candidate countermeasures for the treatment of EVD. Given the waning epidemic, the initial (and, to date, only) phase of the trial was focused only on the evaluation of ZMapp, although the study was designed to provide flexibility to introduce additional treatments under certain situations that are described in the protocol. The Primary Objective of this study was to establish the safety and efficacy of ZMapp in patients diagnosed with Ebola virus infection.

Patients were randomized in the United States, Liberia, Sierra Leone, and Guinea in a 1:1 allocation ratio to optimized standard of care (oSOC) versus oSOC plus ZMapp. A maximum of 200 subjects were to be randomized (100 per treatment arm) in this trial. The primary endpoint for the trial is survival as assessed at Day 28.

Following the first randomized patient on March 13, 2015, the Data and Safety Monitoring Board (DSMB) reviewed interim data on 7 occasions. Following each review, the DSMB indicated that they had no safety concerns and recommended the study continue. In anticipation of study closure due to the absence of EVD, pooled (both treatment groups combined and blinded) outcome data were provided to the U.S. study team by the unblinded statisticians, [name] and [name], on November 25, 2015. These data were used to update the data analysis plan that was prepared prior to the beginning of the trial. The pooled data were updated on December 31, 2015 following submission of 28 day follow-up data for the last person randomized on November 21, 2015.

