3.6 Optimized Supportive Care Descriptions

- Optimized supportive care provided by study day:
 - Intravenous fluids as total volume (continuous variable) and % receiving fluids
 - Intravenous fluids will also be presented by combining all fluids (normal saline and lactated ringers, etc) and presenting in ml/kg to adjust for differences in age and body mass.
 - Other treatments (electrolytes, ventilation, ECMO, supplemental oxygen, medications etc.) as %
- The number of days with supportive care infusions until discharge/death will be summarized.
- Also, for 3-day windows: 1-3, days, 4-6 days, etc. supportive care infusions will be summarized.
- Data will be analyzed both by geographic region and, where applicable, by incorporation of Favipiravir as oSOC.

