 - B. The second alpha level is adjusted using the Haybittle-Peto monitoring procedure:

 α =0.025-(0.001)k, where k is the number of interim looks at the data.

A confidence interval will be computed for the absolute risk difference using Barnard test methodology and confidence level $1-2\alpha$. This will be done for each of the two alpha levels specified above.

- The same approach specified above for Barnard's test, including the two separate alpha levels, will also be performed for Fisher's exact test. A confidence interval for the odds ratio will be computed using the non-central hypergeometric distribution.
- An analysis of time to death will be performed using a log-rank test. In addition, a stratified log-rank test will be performed with 4 strata defined by location and cycle threshold. (See description of stratification variables below). This will be done for each of the two alpha levels specified above. Tests of treatment by subgroup interaction will be performed.

Stratification and subgroup analyses

- Additional analyses will be performed within two strata defined by cycle threshold: ≤22 versus >22 for all subjects. To assess whether there is a treatment by cycle threshold interaction, we will compute the posterior probability that the treatment effect (absolute or relative) differs by cycle threshold.
- Analysis combining the United States, Liberia, and Sierra Leone as one location stratum, while Guinea constitutes the other location stratum. (The standard of care in Guinea typically included favipiravir, which was not the case in the other countries). Note that the protocol initially specified stratified randomization for the USA. However, only one patient in the USA was randomized, which is why the location strata have been changed to USA/Liberia/Sierra Leone vs Guinea. To assess whether there is a treatment by location interaction, we will compute the posterior probability that the treatment effect (absolute or relative) differs by location. An additional sensitivity analysis will exclude the lone patient treated in the United States. The treatment effect within the United States versus West Africa could make interpretation of results more difficult. For example, if the patient was assigned to oSOC and survived, that may simply reflect better oSOC in the United States.

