3.9.2 Safety-Related Outcomes

- SAEs will be summarized and compared between treatment groups as follows:
 - Number and percent of patients experiencing SAEs by treatment group. Test of statistical significance will use Fisher's exact test.
 - For SAEs that are assessed as related to study drug, counts by treatment groups and p-value from zero-inflated negative binomial model.
- Safety line listings by treatment group will be provided for SAEs and "unanticipated problems". Listings will include treatment group label, diagnosis, relatedness to treatment, date of onset, time from treatment to onset, event status (recovered/resolved, recovering/resolving, not recovered/not resolved, recovered/resolved with sequelae, death), date of resolution or death, and EVD status.
- Unanticipated problems

Incidence of "unanticipated problems" will be tabulated for each of the treatment groups. Reports will have similar format as the summary reports for SAEs.

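### The planned between-arm p-value for SAEs judged related to study drug cannot separate a ZMapp effect from unblinded attribution, and should be dropped in favour of descriptive reporting (minor)

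*Combined protocol and SAP*

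**What the plan says.** Section 3.9.2 of the Final Data Analysis Plan opens its SAE list with "SAEs will be summarized and compared between treatment groups as follows". Two comparisons follow. One is Fisher's exact test on the number of patients with any SAE. The other is "For SAEs that are assessed as related to study drug, counts by treatment groups and p-value from zero-inflated negative binomial model". The section also plans line listings that carry relatedness and event status. It gives no alpha level and no decision rule for either test, and it does not say whether the model p-value is a Wald or a likelihood-ratio p-value.

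The features of the trial that bear on the second comparison are stated elsewhere:

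- Final Data Analysis Plan, Section 2: patients were randomized "in a 1:1 allocation ratio to optimized standard of care (oSOC) versus oSOC plus ZMapp", and the "phase of the trial was focused only on the evaluation of ZMapp". There is no placebo.
- Amended protocol, Section 20: "This study follows an open-label randomization design".
- Amended protocol, Section 26.4.1: "The likelihood that the SAE is related to the study agent will be assessed by the investigator", using two categories (reasonable possibility or not). I found no blinded adjudication of causality. The medical monitor's stated task in Section 26.5.1 is expectedness, and the blinded safety office in the earlier Data Analysis Plan prepares reports.

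**The concern.** A between-arm p-value is normally read as evidence about the effect of randomized treatment on the outcome. Here the outcome includes a judgement that the event was caused by the study agent. That judgement is made by someone who knows the arm, about an agent that the control arm does not receive. Two arms with identical SAE experience can therefore have very different related-SAE counts.

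Safety is part of the primary objective. A reader of the safety table could take a small p-value as randomized evidence of harm, or a large or missing one as reassurance. Neither reading would be justified.

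**Working it through.** The plan states no rate, power or p-value for this comparison, so there is no figure to reproduce. The check is whether the p-value can be small when treatment has no effect on SAEs.

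**Inputs from the documents.** Section 2 gives 72 randomized at 1:1, and Section 3.1 excludes one from the primary population. This leaves 71, and I assume 36 on ZMapp and 35 on oSOC. All deaths are SAEs (protocol 26.5.1). Section 3.9 of the Final Data Analysis Plan shows pooled discharge times for 49 patients and clearance intervals for 50. This implies about 71−50=21 to 71−49=22 deaths, or 21/71=30% to 22/71=31%. That is an inference from pooled counts. It makes about 30% a reasonable floor for the any-SAE rate.

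**Assumptions not in the documents.** At most one SAE per patient, a true SAE rate of 30% in both arms, no event attributed on oSOC, 10% or 25% attributed on ZMapp, and a two-sided 0.05 level.

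**Step 1: the test statistic.** With at most one event per patient, the zero-inflation and dispersion terms add nothing to the fit. The likelihood-ratio statistic is then the Poisson one. For k related SAEs v 0:

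LR = 2k·ln(71/36) = 2k × 0.679, referred to chi-square with 1 df.

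| Related SAEs (ZMapp v oSOC) | LR | p (LR) | p (Fisher) |
|---|---|---|---|
| 2 v 0 | 2.72 | 0.099 | 0.49 |
| 3 v 0 | 4.08 | 0.044 | 0.24 |
| 6 v 0 | 8.15 | 0.004 | 0.025 |

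Maximising the zero-inflated likelihood directly gives the same values for 3 v 0 and 6 v 0. So three attributed events are enough for p≤0.05.

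**Step 2: how often this happens with no drug effect.** The chance is P(X≥3) with X ~ Binomial(36, 0.30 × share attributed).

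- Share 10%: p=0.03. P(0)+P(1)+P(2) = 0.334+0.372+0.201 = 0.907, so P(X≥3) = 0.093, about 9%.
- Share 25%: p=0.075. P(0)+P(1)+P(2) = 0.060+0.176+0.250 = 0.487, so P(X≥3) = 0.513, about 51%.

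Replacing the model by Fisher's test would raise the threshold to six events, P(X≥6), which gives 0.07% and 5.0% in the same settings. Those rates still depend on the attribution share, so a change of test does not remove the problem.

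**Step 3: the any-SAE Fisher test.** This test does not use relatedness. Summing binomial probabilities over all tables with p≤0.05, at 36 v 35 and 30% in both arms, gives a size of 3.7% whatever share is called related.

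**Step 4: estimability.** With no related events on oSOC, the log rate ratio has no finite maximum-likelihood estimate. A standard software fit either failed to converge or was singular in all six cases tried (2, 3, 4, 5, 6 and 8 v 0, at 36 per arm), so no Wald p-value was available. These were one-event-per-patient data, in which the extra parameters are barely identifiable. The safe statement is that a Wald p-value may not be obtainable, not that it never is.

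**The case against.** **Real reactions are counted too.** A reader might infer that the p-value reflects attribution alone and carries no information about the drug. The documents do not support that. Genuine ZMapp reactions also enter the count, and the arms themselves are randomized. What stands is that the p-value cannot tell the two sources apart.

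**Control need not be exactly zero.** Section 3.8 says "The standard of care in Guinea typically included favipiravir, which was not the case in the other countries", and Section 3.6 plans summaries "where applicable, by incorporation of Favipiravir as oSOC". If favipiravir counted as study drug, oSOC patients could have related events. The final plan treats it as background care and ZMapp as the only agent evaluated, so this reading is weak. If it did apply, 6 v 1 would give a likelihood-ratio p of 0.051 and 10 v 2 would give 0.018, still with an assessor who knows the arm.

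**The rejection rates depend on assumptions.** This is correct. A reader might infer from higher attribution shares that a false signal is nearly certain. Nothing in the documents supports shares of 50% to 75%. Section 26.4.1 places an event in the unrelated category when there is reasonable evidence for a more likely cause, which will often apply in severe Ebola. The 9% and 51% show the mechanism and do not forecast this trial.

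**The any-SAE test is not fully protected either.** It is free of relatedness attribution but not of open-label reporting. Suppose 30% die in both arms, 25% or 35% of survivors have a non-fatal SAE, and control events are reported half as often. The observed rates are then 47.5% v 38.75%, or 54.5% v 42.25%, and Fisher's test gives p≤0.05 in about 8% or 13% of trials with no true effect.

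**Little depends on it.** This stands. Counts by arm and listings are already planned, infusion reactions are reported descriptively (Section 3.7), and no decision uses the p-value.

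**Conclusion.** The point holds and is minor. As written, Section 3.9.2 attaches a between-arm p-value to an outcome that an unblinded investigator defines by reference to a drug given in one arm only. It can fall below 0.05 with no excess of SAEs: at 3 v 0, and in about 9% to 51% of trials under the stated assumptions (36 v 35, one event per patient, a 30% SAE rate in both arms, 10% to 25% attributed on ZMapp, none on oSOC). The argument itself rests only on the open label, investigator attribution and the absence of study drug on oSOC, all of which are in the documents. The size of the distortion rests on assumptions.

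A reader might go further and infer that the trial's safety conclusion is compromised. It is not: no alpha or stopping rule depends on this p-value, and a comparison that does not use relatedness is already planned. The consequence is limited to how one line of the safety table is read.

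**What to change.** In Section 3.9.2:

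1. Delete the zero-inflated negative binomial p-value for related SAEs.
2. Report related SAEs descriptively in the ZMapp arm as number of patients, percentage and exact 95% CI. For example, 6/36 is 17% (CI 6% to 33%), and 0/36 is 0% (CI 0% to 10%). Keep the counts by arm and the listings as already planned.
3. Keep Fisher's test on patients with any SAE as the randomized SAE comparison that does not depend on relatedness. Add a note that SAE reporting is still open-label.

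The cost is a wording change in the plan. No new data are needed, and no analysis with a decision attached is lost. A descriptive row by arm for non-fatal SAEs regardless of attribution could be added, but it is optional and the correction does not need it.

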3.9.3 Pregnancies

- a listing of subjects pregnant at enrollment

- listing of pregnancies that occurred on study (from randomization to day 58)

3.9.4 Late Clinical Symptoms:

Subjects will be followed for 1 year to evaluate for late symptoms and/or complications. This analysis will be performed at a separate time from the above stated analyses since it must await completion of the one-year follow-up data.

- Number (and % of expected) of subjects with follow up data between day 56 and 365 (i.e. had any follow up visit)
 - Total, and by country
- Number (and % of expected) of subjects with follow up data at Day 365 (i.e. had 1 year follow-up)
 - Total, and by country
- Number (%) with symptoms at 3 month, 6 months, and 1 year
 Table of symptoms present
- Number (%) with complications
- · Listings of complications (if any)
- Pregnancies

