With these considerations in mind, the starting choice of interventions to be entered into and compared in this trial was determined by a consensus of the site investigators performing this study at their individual treatment centers. The most recent deliberations of this group are reflected in Appendix A of this protocol.

Definitions for the Purpose of this Study

Enrolled

For the purpose of collecting data and samples, and reporting SAEs, a subject will be considered enrolled beginning from when the informed consent form is signed until the subject is considered either "discontinued", or "completed".

Discontinued

Subjects are considered discontinued when they meet 1 or more of the following criteria:

- Subject withdraws consent after being dosed and prior to the completion of Day 28 (see Section 19.5)
- Subject is withdrawn after enrollment by investigator (see Section 19.6) including lost to follow-up

Completed

Subjects are considered completed for the main study endpoint when they are followed through Study Day 58 (i.e. 30 days past the primary endpoint measured at Day 28) and complete the final study follow-up visit scheduled for that time. Patients willing to undergo extended follow-up for one year or more (i.e. to determine the incidence of any late onset history or symptoms potentially c/w virologic relapse) will still be considered as having

completed the study if a) they decline this extended follow-up, or 2) choose to discontinue extended follow-up prior to reaching one year past Day 58.

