The day when the subject is enrolled and randomized to their assigned treatment arm is denoted as Study Day 0. The first day after randomization is Study Day 1. Subsequent days will be numbered chronologically through Day 58 of study. For each investigational agent being evaluated a unique schedule of assessments will be developed. The schedule of assessments will be harmonized across comparisons to provide the longitudinal data collection. Patients who agree to extended follow-up past Day 58 to determine the incidence of potential virologic relapse will either be seen in person or contacted via phone on a periodic basis; all study days past Day 58 will be considered Extended Follow-Up assessments. If necessary, and with the patient's verbal consent at the time they agree to extended follow-up, available medical staff and/or records at nearby treatment facilities may be consulted to determine whether the patient has recently been seen for any illnesses potentially consistent with a late onset virologic relapse syndrome. The expected frequency of such periodic assessments will be every 1-3 months up to one full year past Day 58, subject to the patients' wishes and the logistics and feasibility of contacting individual participants on a serial basis.

Table 9: Schedule of Evaluations

Evaluation / Procedure	Screen	Baseline	Follow Up										
Day +/- Window	-1 to 0	0	1	2	3	4	5	6	7	8+ while hospitalized	28- 35	58 ±7	Ext. F/U (Q 1-3 mo.)
ELIGIBILTY/RANDOMIZATION													
Informed consent	Х												
Demographics	Х												
Ebola PCR	-10 to 0												
Randomize subject		Х											
STUDY DRUG ADMINISTRATION	T	r					1		-				
ZMapp™ (if randomized to receive ZMapp™)		X (Day 0 if po	ssible)			ys from dose			ys from dose				
Investigational agents #2		Other in	vestiga	tional a	gents p	er the recent		e trial d	design,	refer to most			
MINIMUM STUDY PROCEDURES (only obtained	while in ti	reatment ur	nit)										
Vital signs		Х	Х	Х	Х	Х	Х	Х	Х	Х	Х	Х	
Record of Optimized Supportive Care		Х	Х	Х	Х	Х	Х	Х	Х	Х			
Assessment of current symptoms/conditions		Х	Х	Х	Х	Х	Х	Х	Х	Х	Х	Х	Х
Ebola PCR with ct		х		x				ry 2-3 days until 1 negative					
Creatinine, Potassium		Х		Х			Х		Х				
OPTIMAL STUDY PROCEDURES (In addition to the	he above.	May include	e any c	or all oj	f the b	elow)	-	-	-				
CBC with differential		Х	Х	Х	Х	Х	Х	Х	Х	Daily	Х	Х	
Ebola PCR with ct		Х	Х	Х	Х	Х	Х	Х	Х	until 2 negative	Х	Х	
Metabolic Panel		Х	Х	Х	Х	Х	Х	Х	Х	Daily	Х	Х	

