21.5.4.4 Extended Follow-Up

Patients will be contacted either in person or by telephone to answer questions according to a special CRF dedicated to eliciting a history of signs or symptoms potentially c/w late onset of a virologic relapse, with particular focus on neurologic symptoms that may represent reemergence of virus from a CNS source.

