3.9.1 Other Secondary Outcomes

In addition to those parameters described in Section 3.6 above, the following will be summarized by treatment group as described:

• Vital Signs: blood pressure, pulse, body temperature, respiratory rate, oxygen saturation – summarized daily by treatment group

• Current symptoms –

Two analyses will be performed to compare the number of symptoms across groups:

- 1. The first analysis of symptoms will compute the average number of symptoms per day during the first 28 days for each patient as well as the average number of days with symptoms. Days with no information on symptoms, including days following the death or discharge of a patient, will be excluded. The groups will be compared using the Wilcoxon rank-sum test. An additional analysis will be conducted using the van Elteren stratified Wilcoxon test on the four strata defined by location (USA/Liberia/Sierra Leone versus Guinea) and cycle threshold (≤22 versus >22).
- The second analysis of symptoms will be identical to the above analysis, but only during the first 3 days. The rationale is that analyses over the entire 28-day period may be difficult to interpret because some patients will be discharged and others may die. Furthermore, the proportion discharged and proportion dying may differ by arm. Restricting attention to the first 3 days will focus the analysis on the initial stage which is free from discharges and some of the deaths.
 - Percent with any symptom
 - Daily summary of number of reported symptoms
 - Summarized for 7 day intervals by treatment group
 - Symptoms at day 28 and day 58 are also summarized.
- Chemistries: measurement of serum creatinine and potassium were required and will be summarized for each 3-day window (i.e. days 1- 3, days 4 6, etc.) by treatment groups, all other chemistries were considered optional and will be summarized as available
 - Additional subgroup analysis will repeat the above for adults and children
 - PCR: blood (note- any CT 40.0 or greater will be treated as negative)
 - \circ summarized for each 3-day window (i.e. days 1- 3, days 4 6, etc.)
 - if more than one PCR is available in a 3 day period for a given subject, the mean result will be used.
 - o summarized as change from baseline for each 3-day window
 - Both of the above will be presented as quantitative (continuous) and qualitative
 - Improvement or worsening of the CT value within the first 72 hours
 - Figure: Kaplan-Meier plot of time to negative Ebola PCR

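### The late-symptom rows in the final analysis plan count symptoms present at 3, 6 and 12 months and do not separate new from persisting ones, so they cannot give the incidence of late-onset symptoms that the protocol sets as the aim

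*Combined protocol and SAP*

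**What the plan says.** **What is to be measured.** In the amended protocol, the secondary objectives (section 17) include long-term follow-up for late-onset history or symptoms that could reflect delayed virologic relapse. Under Definitions for the Purpose of this Study (Completed), the purpose of extended follow-up is "to determine the incidence of any late onset history or symptoms potentially c/w virologic relapse". Section 21, Schedule of Evaluations, also speaks of incidence. Section 22, Analyses, places the question after recovery and initial clearance of virus from plasma, and calls the analysis descriptive.

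**What is collected.** Section 21 states: "The expected frequency of such periodic assessments will be every 1-3 months up to one full year past Day 58". At these contacts, under section 21.5.4.4, patients "answer questions according to a special CRF dedicated to eliciting a history of signs or symptoms potentially c/w late onset of a virologic relapse". Neurological symptoms are singled out for attention there. The Schedule of Evaluations table also marks current symptoms at Day 28-35, Day 58 and extended follow-up.

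**What is tabulated.** Final Data Analysis Plan section 3.9.4, Late Clinical Symptoms, opens with "Subjects will be followed for 1 year to evaluate for late symptoms and/or complications". Its symptom rows are "Number (%) with symptoms at 3 month, 6 months, and 1 year" and "Table of symptoms present". The section also has "Number (%) with complications" and a listing of complications. Section 3.9.1 says "Symptoms at day 28 and day 58 are also summarized", but section 3.9.4 makes no use of those data. By default (section 3), tables are shown by randomised arm.

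**The concern.** The protocol asks how many patients develop something new after recovering. The plan counts how many have symptoms at three times. A patient whose weakness has persisted since the treatment unit and a patient with a new neurological symptom at month 5 add one each to the same cell.

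The symptom rows can therefore err in two directions. Lasting effects of the acute illness raise the count without any relapse. A new symptom that starts and ends between two time points may not enter the count.

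The display by arm adds a risk of misreading. If one arm kept more of the sicker patients alive, and those patients had more lasting symptoms, that arm would show more late symptoms with no relapse at all.

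Amendment E added this follow-up on the DSMB's strong recommendation, after reports of recurrent Ebola virus disease. The new-onset count is what it was added to supply.

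**Working it through.** The plan states no figure for this analysis, so there is none to reproduce. The main check sets the texts side by side.

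| Element | Amended protocol | Final plan, 3.9.4 symptom rows |
|---|---|---|
| Measure | Incidence | Number (%) at 3 months, 6 months, 1 year |
| Which symptoms | Late onset, after recovery and clearance | Symptoms present; no onset rule |
| Data used | Contacts every 1-3 months, with history | Three time points |
| Earlier status | Symptoms marked at Day 28-35 and Day 58 | No link to Day 28 or Day 58 |

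New onset cannot be derived from the right-hand column. It needs each patient's earlier symptom status, which section 3.9.1 summarises separately.

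Two illustrations follow. Their assumptions have no source in the documents.

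**1. Mixing.** The final plan (section 3.9) uses 49 as the denominator for times to viral clearance and to discharge. I take 49 as an approximate number of survivors; it is not the number in extended follow-up. With assumed prevalence *q* of persisting symptoms and one captured relapse in a patient not already counted, the relapse's share of symptomatic patients is 1 / (49*q* + 1):
- *q* = 10%: 1 / (4.9 + 1) = 17%
- *q* = 30%: 1 / (14.7 + 1) = 6%
- *q* = 50%: 1 / (24.5 + 1) = 4%

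**2. Episodes between time points.** Assume that onset is uniform over Days 59-365 (307 days), that each episode lasts *D* days, and that the rows count only symptoms present on Days 90, 180 and 365. For *D* up to 32 days the share present at a time point is 3*D*/307. For 60 days the first time point can catch only the 32 onsets on Days 59-90:
- 7 days: 21/307 = 7%
- 14 days: 42/307 = 14%
- 28 days: 84/307 = 27%
- 60 days: (32 + 60 + 60)/307 = 152/307 = 50%

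If the form for each time point also covers the time since the last contact, fewer episodes are lost and these shares no longer apply. New and persisting symptoms would still be mixed.

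**What a new-onset row could report.** With no new-onset case in 49 patients, the exact two-sided 95% upper limit is 1 - 0.025^(1/49) = 7.3%. That assumes all 49 entered and completed extended follow-up, so the limit would be wider with fewer patients.

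**Timing of contacts.** The first patient was randomised on March 13, 2015 and the last on November 21, 2015 (final plan, section 2). Extended follow-up was approved on November 23, 2015 (Amendment E). On that date the first patient was at Day 255, well past Day 180. Regular contacts from Day 58 cannot be presumed for early enrollees.

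**The case against.** The strongest reply is that section 3.9.4 is broader than its symptom rows and does not claim to be a relapse analysis. Its stated scope is late symptoms and complications, so counting persisting symptoms is not in itself an error. The complications count and listing are not tied to the three time points, so a clinically evident relapse could appear there. The extended-follow-up form elicits history and may already cover the time since the last contact. Section 26 asks about serious adverse events at each contact, and section 3.9.2 of the final plan lists them with onset date and Ebola status, though how far that capture runs past Day 58 is not explicit.

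Much of this stands. A reader might infer that short relapses between time points are simply missed. The documents do not support that: such episodes can drop out of the symptom table but may be recorded elsewhere. The safeguard is weak, because complication is not defined and nothing says that history from between visits enters any table. It also does nothing to separate new from persisting symptoms.

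A second reply is that the analysis is only descriptive. That is true, and it limits the consequence. But an incidence of new onset is also descriptive, and it is the quantity the protocol names.

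A third reply is that a new-onset row brings its own problems: unequal numbers of contacts, possibly different symptom lists on the Day 58 and extended forms, and a comparison by arm that is still among survivors. These points are fair, and the fix has to state them.

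**Conclusion.** The concern holds for the symptom rows. Followed exactly, section 3.9.4 yields prevalence at three times, with persisting and new symptoms together. It cannot give the incidence of late-onset symptoms. This rests on the wording of the documents and needs no assumption.

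The size is not known. The figures of 17% down to 4%, and of 7% to 50%, show what could happen under assumed prevalence, episode length and onset pattern. They are not estimates for this trial. The second set also depends on reading the rows as strict point prevalence, which cannot be settled without the form.

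A reader might also infer that the trial's main result is in doubt. It is not. The analysis is secondary and descriptive, runs separately once one-year data are in, and has no bearing on the 28-day mortality conclusion.

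**What to change.** In section 3.9.4:

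- Add a descriptive row: the number (%) of Day-58 survivors with at least one extended contact who report a new-onset symptom. New onset means absent on the Day 58 form (Day 28 form if Day 58 is missing), or resolved and then recurring, and reported at any extended contact, including history since the last contact.
- Show neurological symptoms separately.
- Give the row overall and by arm with exact 95% confidence intervals. Beside it, give the number of patients, the number of contacts and the follow-up time in each arm.
- Keep the 3-, 6- and 12-month table, labelled as prevalence (persistent plus new).
- State that figures by arm are among survivors and are not a randomised comparison.

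The cost is new wording and a derived variable that links the Day 28 and Day 58 symptom data to the extended contacts, after checking that the forms list matching items. The late analysis runs separately, so the primary analysis is not touched.

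There are two drawbacks. Worsening of a symptom already present at Day 58 does not count as new onset and is seen only in the prevalence table or the complications listing. Early enrollees may have sparse contacts, and an exact binomial interval does not adjust for that, which is why contacts and follow-up time should stand beside it.
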